### 10.5.1.1. Natural log(ACR)/eGFR

Mean ratios of natural log(ACR)/eGFR (Section 6.5.10) are summarized at each time point. The ratio of natural log(ACR)/eGFR by analysis visit is summarized by arithmetic means.

### 10.5.2. Categorical Summaries of Laboratory Results

The number and percentage of patients by laboratory normality and abnormality categories at any time during the study (Normal, Low, High) are summarized by treatment, laboratory category (hematology, chemistry, and urinalysis), and laboratory test. The worst abnormality values are defined as the maximum values while on study treatment, with the exception of magnesium and hemoglobin. The worst abnormal values for magnesium and hemoglobin are defined as the minimum values while on study treatment.

Shift tables summarizing (1) baseline to end of treatment, (2) worst on-treatment to Week 52 (Year 1), and (3) worst on-treatment to Week 104 (Year 2), (4) worst on-treatment to worst off-treatment at Week 52 or Week 104, and (5) baseline to worst on-treatment are presented for lab parameters as appropriate.

An initial set of parameters of specific interest (ALT, AST, ACR) are summarized using shift tables, though additional parameters may be added as appropriate.

In addition, a summary table is provided for number and percentage of patients meeting a following pre-specified threshold level at any time during the study:

- ACR > 3500 mg/g
- Magnesium < 1.3 mEq/L (0.65 mmol/L)
- BNP > 200 pg/mL

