Urine collection for ACR i		X													
Visual acuity			X												
Audiology assessment			X												
PGIC															
CGI-I															
Virus serology	X														
PK samples j															X

Assessment	Wk 24 Day 168±3	Wk 36 Day 252±3	Wk 48 Day 336±3	Wk 52 Day 364-6	Wk 64 Day 448±5	Wk 76 Day 532±5	Wk 88 Day 616±5	Wk 100 or End of Treatment k Day 700±3	Wk 104 or Follow-up k Day 728-6
Informed consent									
Inclusion/ exclusion									
Demographics and baseline disease characteristics									
Concomitant medications	X	X	X	X	X	X	X	X	X
Medical history									
Height	X	X	X	X	X	X	X	X	X
Weight in clinic	X	X	X	X	X	X	X	X	X
Weight at home	X	X	X	X	X	X	X	X	X
Dispense weight diary	X	X	X	X	X	X	X	X	X
Collect/review weight diary	X	X	X	X	X	X	X	X	X
ECG			X	X				X	X
Echocardiogram 									
Vital sign measurements	X	X	X	X	X	X	X	X	X
Physical exam	X	X	X	X	X	X	X	X	X
Pregnancy test for WOCB pf	X	X	X	X	X	X	X	X	X
Study drug administration									
Dispense study drug	X	X		X	X	X	X	X	
Collect study drug	X	X	X		X	X	X	X	
Telephone contact									
Adverse event collection	X	X	X	X	X	X	X	X	X
Genetic testing 									
Clinical chemistry (incl. eGFR)	X	X	X	X	X	X	X	X	X
BNP and NT-proBNP	X	X	X	X	X	X	X	X	X
IGF-1 and serum ketones	X	X	X	X	X	X	X	X	X
Hemoglobin A1c			X					X	
Hematology	X	X	X	X	X	X	X	X	X
Urinalysis and microscopy	X	X	X	X	X	X	X	X	X
Urine collection for ACR 	X	X	X	X	X	X	X	X	X
Visual acuity			X					X	
Audiology assessment			X					X	
PGIC	X		X		X			X	X
CGI-I	X		X		X			X	X
Virus serology									
PK samples 									

- a Total Screening period should not exceed 6 months.
  - b Screen B visit should be no more than 30 days prior to Day 1.
  - c Day 1 is the day of administration of the first dose. **On Day 1, all procedures should be performed before study drug administration.**
  - d Screening eligibility procedures do not need to be repeated on Day 1; however, a review of any changes in eligibility criteria should be evaluated prior to Day 1 procedures, and a urine pregnancy test should be performed for WOCBP.
  - e An echocardiogram performed at the Screen A visit or within 6 months prior to Day 1 may be used to determine eligibility.

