## **6. GENERAL CONSIDERATIONS FOR DATA ANALYSES AND HANDLING**

The efficacy and safety analyses use the analysis sets defined in Section 6.3. Patient listings (as appropriate) of all analysis data that support summary tables and/or figures are provided along with their source data. The summary tables do not include measurements from patients excluded from the pre-defined analysis sets or extra measurements (such as unscheduled or repeat assessments) not closest to the target study day unless specified otherwise, but the patient listings do include these data. Missing data are not imputed, unless otherwise specified. In general, patient listings are sorted by patient number and assessment date (time and parameter, as applicable). Any laboratory value (including eGFR), vital sign assessment, or ECG value collected after starting dialysis or after receiving a kidney transplant is considered invalid and will be treated as missing.

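### The worst on-treatment laboratory value is the maximum for every test except magnesium and hemoglobin, which is the wrong direction for any other test where a fall is the harm

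*SAP*

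**What the plan says.** SAP Section 10.5.2 opens with a count of patients in each normality category, "at any time during the study (Normal, Low, High"), by treatment and by test, for hematology, chemistry and urinalysis. The next two sentences of the same paragraph define the worst value: "The worst abnormality values are defined as the maximum values while on study treatment, with the exception of magnesium and hemoglobin". Then: "The worst abnormal values for magnesium and hemoglobin are defined as the minimum values while on study treatment".

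The following paragraph lists five shift tables. Four of them use a worst on-treatment value, ending with "5) baseline to worst on-treatment are presented for lab parameters as appropriate". On which tests these cover, the section says: "An initial set of parameters of specific interest (ALT, AST, ACR) are summarized using shift tables, though additional parameters may be added as appropriate".

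eGFR is treated as a laboratory value. The schedule of assessments in Section 4.5 has a row headed "Clinical chemistry (incl. eGFR"), and Section 6 has a handling rule that begins "Any laboratory value (including eGFR), vital sign assessment, or ECG value collected after starting dialysis". Section 8.2 says that eGFR falls as the disease progresses, so a low value is the adverse one.

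**The concern.** The rule is closed: two named tests take the minimum and all others take the maximum. Naming two exceptions shows that direction was considered, but the list stops at two. For any other test where a fall is the harm, the maximum is the patient's best on-treatment value. For a test that can be harmful in either direction, it ignores the low side.

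Safety assessments through Week 52 and Week 104 are listed among the primary endpoints (Sections 3.1.1.1 and 3.1.2.1). If the rule drives the categorical tables, a between-arm difference in low laboratory values would be largely hidden in them. The rest of Section 10.5.2 gives little backup: its threshold table (ACR, magnesium, BNP) has one low-side criterion, magnesium.

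**Working it through.** The plan gives no figure here to reproduce. The check reads the rule against the tables that may use it, then applies it to assumed data.

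**1. Where the rule reaches output**

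| Output in Section 10.5.2 | Uses the worst value? | Consequence |
|---|---|---|
| Shift tables for ALT, AST, ACR | Yes, in four of the five | None: a rise is the harm for all three, so the maximum is right |
| Shift tables for tests added later | Yes, in four of the five | Wrong direction for any low-is-harm test other than magnesium and hemoglobin |
| Normal/Low/High counts | Not settled | If yes, Low requires every on-treatment value to be low |

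Two things favour applying the rule to the Normal/Low/High counts. It follows that sentence in the same paragraph, and it is the section's only way of reducing repeated values to one. One thing points the other way: the counts are for any time during the study, while the rule is restricted to time on treatment. The text leaves the question open.

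**2. Direction, illustrated with eGFR**

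These data are assumed: an adult male, not black, age held at 30, with on-treatment creatinine of 1.3, 1.5, 1.8 and 2.2 mg/dL. The Section 6.5.6 adult formula, for creatinine above 0.9, is eGFR = 141 × (Scr/0.9)^−1.209 × 0.993^30.

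- The four eGFR values are 73.2, 61.6, 49.4 and 38.8.
- The maximum is 73.2, category 2 in SAP Table 5. The minimum is 38.8, category 3b.
- The fall from the first value is 1 − 38.8/73.2 = 47%.
- The worst creatinine under the rule is 2.2, from the visit with the lowest eGFR. The rule would therefore take worst creatinine and worst eGFR from opposite visits.

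**3. Size, if the rule assigns Normal/Low/High**

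The maximum is below the lower limit only if all values are. A patient low at 3 of 13 visits and normal at the rest is counted Normal.

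Inputs:
- n = 13 post-baseline on-treatment visits (Section 4.3.1 for Year 2; visit list in Section 8.8.1 without visit 0).
- p = chance that a single value is low. This is assumed, at 20%, with lower values shown for range.
- ρ = within-patient correlation. Section 4.3.1 assumes 0.7 for eGFR; using it for other tests is an assumption.

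Under independence:
- All low: 0.2^13 = 8.2 × 10^−10.
- At least one low: 1 − 0.8^13 = 94.5%.

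With correlation, I used an exchangeable normal-threshold model. Let z = Φ⁻¹(p), which is −0.842 at p = 0.20. Given a standard normal patient effect b, the chance of a low value is q(b) = Φ((z − √ρ·b)/√(1 − ρ)). All low is the mean of q^13 over b. At least one low is 1 minus the mean of (1 − q)^13.

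| p | ρ | All 13 low | At least one low |
|---|---|---|---|
| 20% | 0 | below 0.001% | 94.5% |
| 20% | 0.7 | 2.4% | 53.1% |
| 20% | 0.9 | 7.8% | 37.2% |
| 10% | 0.7 | 0.7% | 33.9% |
| 5% | 0.7 | 0.2% | 20.6% |

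At p = 20% and ρ = 0.7, 2.4/53.1 = 4.5% of patients with a low value would be counted as Low.

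**The case against.** The strongest reply is that no committed table goes wrong. The only tests named for the shift tables are ALT, AST and ACR, and the maximum suits all three. The worst-value sentences may simply define a term for the shift tables that follow. A reading that nearly empties the Low column is less natural than one in which any low value counts. This has force: the text does not say that the rule governs the Normal/Low/High counts. But if it does not, the section has no rule for a patient who is Low at one visit and High at another, and the definition still fails for any low-is-harm test added to the shift tables.

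A reader might infer that the patient's best eGFR is certain to be reported as the worst. The documents do not support that. No worst-value table is committed for eGFR, and no reference range for a Low eGFR is given. eGFR declines are analysed from all on-treatment values in Sections 9.1.2 and 9.4.1, and Section 9.1.3 gives the distribution of decreases.

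A reader might also infer that falls in other tests would go unseen altogether. They would not: Section 10.5.1 summarizes selected tests by visit and arm and flags values below normal in the listings. These are weaker substitutes for a by-arm count, because the summaries average over patients and the listings do not compare arms.

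Finally, the near-zero probability under independence should not be taken as the size of the problem. Repeated values within a patient are correlated, and the gap at ρ = 0.7 is far smaller.

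**Conclusion.** The stated rule is wrong for any test where a fall is the harm, other than magnesium and hemoglobin, and it is blind to low values where both directions matter. Whether this reaches a table depends on two points the SAP leaves open: whether the rule assigns Normal/Low/High, and which tests are added to the shift tables.

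If it does assign the category, about 2.4% of patients would be counted as Low where 53% had at least one low value. That rests on an assumed 20% chance per visit, 13 visits and a correlation of 0.7. The contrast varies with these assumptions, but a clear gap remains across the range shown. The number of tests affected cannot be counted, because the documents do not itemize the hematology and chemistry panels.

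The effect is confined to descriptive safety tables, for which Section 10 plans no formal testing. The primary, key secondary and kidney-failure analyses do not use the rule. It should be corrected before the safety tables are produced, but it does not threaten the efficacy conclusions.

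**What to change.** In SAP Section 10.5.2:

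- Define worst by the direction of concern for each test: the minimum where low is harmful (eGFR, if tabulated, with magnesium and hemoglobin), the maximum where high is harmful, and separate lowest-value and highest-value rows where both matter.
- Apply that definition to every shift table that uses a worst on-treatment value, including for tests added later.
- State that the Normal/Low/High table counts a patient as Low if any value in the period is low and as High if any is high, so that a patient may appear in both. State whether the period is the whole study or time on treatment.

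The cost is SAP wording, a direction flag per test in the programs and some extra table rows. No new data are needed.

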#### 10.5.2.1. Transaminases

Evaluation of Drug-Induced Serious Hepatotoxicity (eDISH) plots are generated for ALT and AST versus TBL.

The number and percentage of patients meeting the following thresholds, which are consistent with FDA guidance, are summarized by the maximum dosage received:

**Table 9. Pre-Specified Threshold Levels for Transaminases**

Lab Parameter	Threshold
ALT, AST	$\geq 3 \times$ upper limit of normal (ULN) and $< 5 \times$ ULN
	$\geq 5 \times$ ULN and $< 10 \times$ ULN
	$\geq 10 \times$ ULN and $< 20 \times$ ULN
	$\geq 20 \times$ ULN
	$\geq 5 \times$ ULN for more than 2 weeks
TBL	$\geq$ ULN and $\leq 1.5 \times$ ULN
	$> 1.5 \times$ ULN and $\leq 2 \times$ ULN
	$> 2 \times$ ULN
ALT, /AST, TBL	ALT or AST $> 3 \times$ ULN and Total bilirubin $> 1.5 \times$ ULN

Lab Parameter	Threshold
	ALT or AST > 3×ULN and Total bilirubin > 2×ULN
ALT, AST, TBL, INR	> 3 × ULN and (TBL > 2 × ULN or INR > 1.5)
ALP	> 1.5 × ULN

A summary table that includes frequencies and percentages of patients that meet any of the above criteria at any time during the study is provided. A listing of subjects with abnormal ALT, AST, or TBL will also be provided.

## 10.6. Vital Signs

Vital signs assessments include systolic blood pressure (SBP, mmHg) and diastolic blood pressure (DBP, mmHg), body temperature (°C), heart rate (HR, bpm), height (m), weight (kg), and BMI (kg/m^2). Vital signs are summarized at baseline and at each time point along with the change from baseline by treatment. Boxplots and line graphs of change from baseline over time for blood pressure are plotted.

### 10.6.1. Body Weight

Body weight, as collected during each in-office visit, is summarized using descriptive statistics for observed results and change from baseline at time point. In addition, number and percentage of patients experiencing a five pound (2.3 kilogram) or greater increase in weight are summarized by time point. Boxplots and line graphs of change from baseline over time for weight are plotted.

## 10.7. Physical Examination

Physical exam results are listed.

## 10.8. Electrocardiogram

Electrocardiogram (ECG) data, such as clinical interpretation of ECGs, heart rate and interval assessments of PR, QRS, and QT are collected on the eCRF. QTcF is calculated for analysis (Section 6.5.8). Descriptive statistics for observed values and change from baseline at each time point are presented for these 12-lead ECG interval assessments. In addition, number and percentage of patients with any abnormal values (i.e., above a pre-specified threshold) at any time during the study are summarized by time point and overall. The pre-specified levels of ECG QTc thresholds are consistent with FDA guidance:

**Table 10. Pre-Specified Threshold Levels for ECG Parameters**

ECG Parameter	Pre-Specified Level
PR	> 200 msec
QTcF	> 450 and ≤ 480 msec
	> 480 and ≤ 500 msec
	> 500

ECG Parameter	Pre-Specified Level
	Change from baseline: $>30$ and $\leq 60$ msec
	Change from baseline: $> 60$ msec
Heart rate	$< 40$ beats/min
	$< 100$ beats/min

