### 4.3. Sample Size Considerations

The Year 1 and Year 2 endpoints are not independent hypothesis sets. The endpoints are analyzed using a combination of the Bonferroni and fixed-sequence approaches for type 1 error control (Section 8.4).

The protocol specified enrollment of approximately 150 patients in the Phase 3 cohort. Actual enrollment in the Phase 3 cohort was 157. Sample size calculations for each year based on the actual number of patients enrolled are presented below.

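### The second heart-rate row of SAP Table 10 (below 100 beats/min) appears to have its sign reversed, so the ECG abnormality table has no high-rate flag

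*SAP*

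**What the plan says.** SAP Section 10.8 states that the ECG summaries will include the "number and percentage of patients with any abnormal values (i.e., above a pre-specified threshold) at any time during the study", presented at each time point and overall. The levels are in Table 10. PR and QTcF have upper limits only, and the QTcF levels are split into separate bands. Heart rate has two rows: one for rates below 40 beats/min and one reading "< 100$ beats/min". There is no third heart-rate row.

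On where the levels come from, the section says only this: "The pre-specified levels of ECG QTc thresholds are consistent with FDA guidance". It gives no source for the heart-rate levels.

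Heart rate is also a vital sign under Section 10.6, where "Vital signs are summarized at baseline and at each time point along with the change from baseline by treatment". No threshold is attached to it there. Neither the SAP addendum nor the COVID-19 protocol addendum changes Table 10.

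**The concern.** A table of abnormal values should separate unusual readings from ordinary ones. As printed, the second heart-rate row does the reverse: a rate of 70 is counted as abnormal and a rate of 130 is not. The row also makes the first one redundant as a separate category, because every rate below 40 is below 100 as well.

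At stake is one line of a descriptive safety table in the clinical study report. If the programmers follow the SAP literally, that line will sit near its ceiling in both arms, cannot show a difference between them, and leaves the table without a direct count of patients with a fast rate.

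**Working it through.** The plan states no figure to reproduce. The check is mainly logical, with a calculation added for scale.

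**Step 1. Apply the two printed rows to every possible rate.**

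| Heart rate (beats/min) | Row 1: below 40 | Row 2: below 100 |
|---|---|---|
| under 40 | flagged | flagged |
| 40 to 99 | not flagged | flagged |
| 100 or more | not flagged | not flagged |

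Row 2 contains row 1, and no rate of 100 or more is flagged by either row. This needs no assumption. The QTcF rows behave differently: the absolute bands (above 450 to 480, above 480 to 500, above 500) and the change bands (above 30 to 60, above 60) do not overlap, and each marks a value that is too high.

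**Step 2. Compare with the counting rule.** Section 10.8 equates abnormal with above a threshold. Neither heart-rate row fits that. The mismatch with the below-40 row shows that the wording is loose, so it cannot by itself settle which sign was meant for the second row. The nesting in step 1 and the missing upper limit carry the argument.

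**Step 3. Scale, on one ECG.** The documents give no heart-rate distribution. Assume a normal distribution with mean m of 65 to 85 and SD s of 10 to 15 beats/min, with rates recorded as whole numbers.

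- Share flagged as printed: P(rate < 100) = Φ((99.5 − m)/s).
- Share flagged with the sign reversed: P(rate > 100) = 1 − Φ((100.5 − m)/s).

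| m | s | Below 100 (as printed) | Of 157 patients | Above 100 (sign reversed) |
|---|---|---|---|---|
| 65 | 10 | Φ(3.45) = 0.9997 | 157.0 | 0.0002 |
| 75 | 12 | Φ(2.04) = 0.9794 | 153.8 | 0.0168 |
| 85 | 15 | Φ(0.97) = 0.8331 | 130.8 | 0.1507 |

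The 157 comes from SAP Section 4.3 ("Actual enrollment in the Phase 3 cohort was 157") and is used for scale only. The safety population is limited to patients who were dosed.

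**Step 4. The any-time count.** The assessment schedule has post-baseline ECGs at Weeks 48, 52, 100 and 104. A patient with all four avoids the printed flag only if every one is at 100 or more.

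- If a patient's four readings were fully correlated, the share flagged would equal the single-ECG share, so 83% at the low end.
- If they were independent, the low end would be 1 − (1 − 0.8331)⁴ = 0.9992.

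The truth lies between these, so the overall count is at least as high as the single-ECG figures.

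**The case against.** The strongest reply is that the row still carries information. Section 6.2 bases categorical percentages on patients with available data, and Section 6.5.4 selects one reading per visit window. At each time point, then, 100% minus the printed row's percentage is the share at 100 or above. That stands for the by-visit columns. It does not rescue the overall column, whose complement contains only patients who were at 100 or above on every ECG.

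A reader might infer that fast heart rates would go unreported altogether. The documents do not support that. Heart rate is summarized at each time point with its change from baseline, Section 6.2 includes the maximum among the descriptive statistics, the clinical interpretation of ECGs is collected, and a fast rate reported as an adverse event would enter the AE tables. What is missing is an explicit high-rate count in Table 10.

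A reader might also take it as fact that virtually all patients would be flagged. That depends on an assumed distribution, and on one ECG the low end of the range is 83%.

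Finally, the sign could have been misread when the PDF was converted. This cannot be excluded from the text alone. It looks unlikely, because the greater-than signs in the change-from-baseline rows, in the same part of the split table, came through correctly. The source page settles it.

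**Conclusion.** The point holds as an apparent sign error in one row of a descriptive safety table. That the two rows are nested and that no row flags a high rate follow from the table itself, subject only to confirming the printed sign. The size is conditional: about 83% to 99.97% of patients flagged on a single ECG under the assumed mean and SD, and no lower for the any-time count, against about 0.02% to 15% of single ECGs if the row were a high-rate flag.

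The consequence is small. SAP Section 10 plans no formal testing of safety data, and no efficacy analysis, power figure or significance level depends on Table 10. The point is worth correcting because the table will be programmed and the correction is nearly free.

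**What to change.** 1. Check the heart-rate rows of Table 10 on the source page.
2. If the second row prints a less-than sign there, correct it to a high-rate flag, > 100 beats/min. Only the sign changes; the 100 is the table's own figure.
3. In Section 10.8, replace above with outside in the description of an abnormal value, so that the below-40 row fits the text as well.
4. Confirm that the table shells and programs use the corrected row.

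The cost is one character in the table, one word in the text and a check of the programming. No data collection or other analysis changes.

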### 10.9. Visual Acuity

Patients with normal visual acuity are those with 20/20 vision or less (e.g., 20/15, 20/10, etc.) in both eyes. Findings from visual acuity examinations are listed. Observed logMAR value and its change from baseline are summarized descriptively by time point. In addition, shift tables are generated by treatment, visit, and normal versus abnormal visual acuity values.

### 10.10. Audiology Assessment

Findings from audiology assessments are listed. The average pure-tone hearing threshold for each ear is measured using the automated pure tone test. Patients with normal pure-tone hearing are those with pure tone audiometry (PTA)  $< 25$  decibels in both ears. Any patient with  $\geq 25$  decibel hearing in either ear are considered to have audiology impairment. The number and percentage of patients with normal or impaired hearing in at least one ear is summarized by time point. In addition, number and percentage of patients within each of the following categories will be summarized at baseline, Week 48, and Week 100:

- PTA  $\leq 25$  dB
- 25 dB  $< PTA \leq 40$  dB (mild to moderate hearing loss)
- 40 dB  $< PTA \leq 70$  dB (moderate to severe hearing loss)
- 70 dB  $< PTA \leq 85$  dB (severe to profound hearing loss)
- PTA  $> 85$  dB (profound hearing loss)

Descriptive statistics for observed values and change from baseline in hearing threshold for each ear (i.e., right and left) are presented.

